4.1. Overall Design

Section 1.2 illustrates the study schema.

Study JPCS is a multicenter Phase 1b/2 study with 3 parts. Parts A and B are in patients with any relapsed/refractory solid tumor that has progressed on standard treatments and for whom experimental therapy with abemaciclib in combination with temozolomide or in combination with temozolomide and irinotecan is deemed medically appropriate by the investigator. Part C will exclusively enroll participants with relapsed/refractory neuroblastoma and for whom experimental therapy with abemaciclib in combination with dinutuximab, GM-CSF, irinotecan, and temozolomide is deemed medically appropriate by the investigator. Due to global differences in the standard of care for this population, the trial will enroll patients to Part C only in North America and Australia.

The total sample size for the study is dependent on the incidence of DLTs in all parts and responses in Part C. The study will enroll approximately 30 to 117 patients (see Section 9.2). Patients in Parts A and B must be ≤ 18 years of age and weigh ≥ 10 kg (with body surface area [BSA] ≥ 0.5 m 2). Patients in Part C must be <21 years of age (for patients with a starting abemaciclib dose of 30 mg/m 2 BID, BSA must be ≥ 0.3 m 2). The trial will be conducted following a 3+3 dose escalation scheme for Parts A and B and Simon's two-stage design (Simon 1989) with a dose finding component for Part C:

- Part A: abemaciclib in combination with irinotecan and temozolomide
- Part B: abemaciclib in combination with temozolomide
- Part C: abemaciclib in combination with dinutuximab, GM-CSF, irinotecan, and temozolomide.

Part A will be executed first to confirm the MTD of abemaciclib in combination with irinotecan and temozolomide. The MTD is defined as the highest dose level at which less than 33% of patients experience a DLT during Cycle 1. After the MTD of abemaciclib in Part A has been determined, Parts B and C will open. As Part B reduces cumulative exposure to myelosuppressive agents, it will enroll at a starting dose one level higher than the abemaciclib MTD in Part A (not to exceed 115 mg/m 2). Since Part B will not start at the lowest dose level (unless the lowest dose level of Part A is not tolerated), this sequential design has potential to minimize the number of patients necessary to complete Part B. The dose escalation/de-escalation method for abemaciclib in Parts A and B is described in detail in Section 4.1.1. Part C will utilize the MTD for the combination of abemaciclib, irinotecan, and temozolomide identified in Part A and the standard dosing of dinutuximab and GM-CSF (Mody et al. 2020) as the starting dose. Part C consists of two stages that will evaluate (1) safety and tolerability and (2) anti-tumor activity of the combination (details in Section 4.1.2).

Dose-limiting toxicities will be evaluated during the 21 days of treatment in Cycle 1. After the MTD has been identified, an expansion cohort for each part will be enrolled to further inform safety and PK and to confirm the tolerability in additional patients.

The cycle length is 21 days. Patients will continue study treatment until at least one of the discontinuation criteria is met (Section 7). Continuation on chemotherapy beyond Cycle 12 will be up to the investigator's discretion and the individual patient's situation. Prior to continuing the patient on chemotherapy beyond Cycle 12, the investigator should discuss with the Lilly clinical research physician/clinical research scientist (CRP/CRS).

The primary objective in Parts A and B is to determine the RP2D of abemaciclib in combination with irinotecan and temozolomide (Part A), and abemaciclib in combination with temozolomide (Part B) in patients with relapsed/refractory solid tumors. The secondary objectives include the assessment of the safety profile, preliminary anti-tumor activity, and abemaciclib acceptability and palatability. **CCI**

The co-primary objectives in Part C are to evaluate the safety, tolerability, and anti-tumor activity of abemaciclib in combination with dinutuximab, GM-CSF, irinotecan, and temozolomide in patients with relapsed/refractory neuroblastoma. The secondary objectives include the assessment of DoR, CBR, DCR, and PFS by investigator assessment, and evaluation of drug product acceptability and palatability. **CCI**

4.1.1. Dose Escalation Design for Parts A and B

The dose will be escalated following assessment of toxicity using the standard scoring system, Common Terminology Criteria for Adverse Events (CTCAE) Version 5.0, established by the National Cancer Institute (NCI).

In Part A, patients will begin abemaciclib at Dose Level 1 (70 mg/m^2). After the dose escalation of Part A is completed, one dose level higher than the MTD of abemaciclib in Part A will be used as the starting dose in the dose escalation of Part B, but will not exceed 115 mg/m^2 BID. Three patients are planned for treatment at each dose level; however, the exact number of patients treated at a specific dose level depends on the number of patients within the cohort who experienced a DLT.

Patients will be considered DLT-evaluable if they have either completed the DLT-observation period and received at least 75% of planned doses of each study drug in Cycle 1 or have discontinued study treatment or study participation before completing Cycle 1 due to a DLT or received less than 75% of planned Cycle 1 doses due to drug-related toxicity. Non-evaluable patients may be replaced to ensure that enough patients complete 1 cycle unless accrual to that cohort has stopped due to a DLT.

Following the 3+3 dose escalation scheme, if 0 of 3 patients at a given dose level experience first cycle DLT, the subsequent cohort will enroll at the next higher dose level.

- If 0 of 3 evaluable patients experience a DLT, but safety concerns are present, 3 additional patients may be added to the same dose level cohort to provide additional data following discussion between the investigators and the sponsor.

If 1 of 3 evaluable patients in a cohort experience a DLT, the cohort will be expanded to include 6 patients.

- The dose escalation can proceed if <2 out of 6 evaluable patients experience a DLT.

- If a DLT is observed in ≥ 2 out of a maximum of 6 evaluable patients at any given dose, a safety review will be triggered, dose escalation will cease, and the next lower dose will be considered the MTD.

If the starting dose level of abemaciclib 70 mg/m² BID is not tolerated in Part A, the A-1 dose level of 55 mg/m² BID of abemaciclib will be explored. If 55 mg/m² of abemaciclib is not tolerated in Part A, a thorough safety review will be conducted in collaboration with investigators to weigh the benefits and risks of starting Part B. If the combination is deemed to be not tolerable due to overlapping toxicity of abemaciclib plus temozolomide or abemaciclib alone, the study will not proceed to Parts B or C. However, if the combination was not tolerable due to overlapping toxicity of abemaciclib plus irinotecan (e.g. DLTs of diarrhea), Part B using 55 mg/m² of abemaciclib as the starting dose may proceed.

In this study, intrapatient dose escalation is not permitted.

The RP2D of abemaciclib will be defined based on the totality of safety, tolerability, and PK results. Dose-limiting toxicities and dose selection decisions will be made after discussion between the investigators and the sponsor.

The RP2D from each part will be confirmed in expansion cohorts for each combination. Expansion cohorts will enroll 6 patients. In both study parts, upon completion of a thorough safety review, additional patients can be enrolled if necessary to confirm safety. Examples may include testing a lower dose in 6 additional patients if DLTs are experienced by at least 2 of 6 patients in the initial expansion cohort to further confirm tolerability of prolonged treatment.

4.1.2. Two-stage Design for Part C

Part C consists of two stages to first evaluate the safety and tolerability and then the anti-tumor activity of abemaciclib in combination with chemoimmunotherapy. The design is briefly described below with a figure immediately following.

Stage 1

Stage 1 starts with a dose optimization to identify MTD. Specifically, it will initially enroll 3 patients at 55 mg/m² (i.e., the MTD for abemaciclib in combination with irinotecan and temozolomide in Part A plus dinutuximab and GM-CSF) and use 3+3 rules to guide dose decision. During MTD identification, if 55mg/m² is deemed intolerable, then a lower abemaciclib dose of 30mg/m² (keeping the other drugs the same) will be explored. If this lower dose level is deemed intolerable, Arm C will be terminated due to intolerance.

In addition to the safety assessment, the anti-tumor activity will be measured by objective tumor response. If MTD is declared, an expansion cohort will enroll at the MTD to confirm the tolerability while evaluating the preliminary anti-tumor activity. In the expansion cohort, up to [REDACTED] patients may be simultaneously enrolled. Stage 1 will enroll up to [REDACTED] DLT-evaluable patients at the identified MTD. If none of the following stopping rules are triggered, the MTD will be confirmed as RP2D and Part C will move to Stage 2.

- Rule A: stop for toxicity if [REDACTED] CCI of the DLT-evaluable patients experience DLT.
- Rule B: stop for intolerance if [REDACTED] CCI patients discontinue due to treatment-related AE before completing [REDACTED] cycles.

- Rule C: stop for insufficient evidence of anti-tumor activity if < ^{cc1} of ^{cc1} patients are responders (i.e., have objective tumor response, including a best overall response of complete response [CR], partial response [PR] or minor response [MR] per INRC).

De-escalation during cohort expansion: If 55mg/m² is declared the MTD, but either stopping Rule A or B is triggered in the cohort expansion, subsequent patients will be treated at 30mg/m² and those at the 55 mg/m² dose may be dropped to 30 mg/m² upon investigator's discretion. Part C will continue to enroll until there are ^{cc1} total patients treated at 30 mg/m² with a minimum of ^{cc1} newly enrolled DLT-evaluable 30mg/m² patients. If no stopping rules are triggered, the dose combination with abemaciclib at 30 mg/m² is the RP2D and Part C will move to Stage 2.

Stage 2

An additional ^{cc1} patients will be enrolled at the RP2D in Stage 2. Among the ^{cc1} evaluable patients treated in Stages 1 and 2 at the RP2D, if there are ^{cc1} responders, then there is insufficient evidence of anti-tumor activity. If ^{cc1} of the patients are responders, then it is reasonable to conclude that the drug combination has promising anti-tumor activity that could warrant further study.

The figure below illustrates the Part C design.

Statistical details for the two-stage design are provided in Section 9.

4.1.3. Dose-Limiting Toxicity Determination and Maximum Tolerated Dose Definition

A DLT is defined as any of the events according to the NCI CTCAE version 5.0 below if both the following criteria are met:

- The event occurs during the DLT observation period of Cycle 1, between Days 1 and 21, and,
- The event is clinically significant and either definitely, probably, or possibly related to abemaciclib or the combination treatment following discussion between the investigator and Lilly CRP/CRS.

Investigators, together with the Lilly CRP/CRS, can declare a DLT if a patient experiences a significant toxicity deemed to be dose-limiting.

In the event of any Grade 5 AE, enrollment will be suspended, and a thorough safety review will be performed prior to resuming enrollment.

If a patient receives <75% of any planned Cycle 1 study drug doses due to drug-related toxicity, the toxicity will be declared a DLT.

Nonhematological events:

With the exceptions listed below, all Grade ≥ 3 nonhematological AEs will be considered a DLT.

Exceptions:

- Grade 3 diarrhea controlled with supportive care and lasting <72 hours;
- Acute irinotecan-associated diarrhea lasting <7 days and controlled with supportive care;
- Grade ≥ 3 nausea, vomiting, or constipation that is manageable with supportive care and lasts <72 hours;
- Grade 3 mucositis/stomatitis of <72 hours duration;
- Grade 3 fever or infection;
- Grade ≥ 3 electrolyte abnormality that lasts <72 hours, is not clinically complicated, and resolves spontaneously or responds to conventional medical interventions;
- Grade ≥ 3 amylase or lipase that is not associated with symptoms or clinical manifestations of pancreatitis; or
- Aspartate aminotransferase (AST)/ALT elevation resolving to eligibility criteria within 7 days;

Hematological events:

- Cycle Delay: a >14-day delay in the start of a subsequent cycle because of neutropenia or thrombocytopenia in the absence of bone marrow disease progression seen on clinically indicated bone marrow biopsy (if performed).
Note: Patients who experience dose-limiting neutropenia and/or thrombocytopenia will have these events reviewed by the sponsor to discuss attribution (bone marrow disease [baseline and subsequent, if performed and clinically indicated] versus study drugs). Patients with bone marrow disease progression will not be considered to have dose-limiting hematological toxicities.
- Grade ≥ 3 thrombocytopenia with clinically significant bleeding; or
- Grade ≥ 4 neutropenic fever.

Note: Lymphopenia is not considered a DLT unless clinically significant.

Aggregate data will be reviewed and taken into consideration for determining the RP2Ds.

The I3Y-MC-JPCS Toxicity Documentation Form must be completed and sent to Lilly for each patient during the DLT period in order for timely evaluation of DLTs.

- If a DLT is experienced during the DLT evaluation period, the I3Y-MC-JPCS Toxicity Documentation Form should be completed and sent to Lilly within 3 days of becoming aware of the DLT.

- If no DLT is experienced, the form should be completed and sent 3 days after the DLT evaluation period has ended.

4.2. Scientific Rationale for Study Design

The overall rationale for the study design is described in the Introduction section under Study Rationale (Section 2.1) and in Statistical Considerations (Section 9). Dose selection details can be found in Section 4.3.

4.3. Justification for Dose

4.3.1. Abemaciclib

Abemaciclib has demonstrated efficacy with a tolerable safety profile in advanced breast cancer at a monotherapy dose of 200 mg BID, and in combination with fulvestrant or aromatase inhibitors at a dose of 150 mg BID (Dickler et al. 2017; Goetz et al. 2017; Sledge et al. 2017; Johnston et al. 2019). Across all pivotal registration trials for abemaciclib in adult patients with cancer, no clinically meaningful effect of age, body weight, sex, or race/ethnicity on the PK of abemaciclib has been identified. Therefore, in adults, abemaciclib is dosed without adjustment for body size.

In pediatric patients, the enzyme largely responsible for the clearance of abemaciclib (CYP3A4) reaches maturity after the first year of life (Bartelink et al. 2006). Between the age of 1 to 12 years, CYP-mediated metabolism is largely dependent on liver volume, which is better correlated with body surface area (BSA) rather than body weight (Bartelink et al. 2006). As such, in pediatrics, doses will be scaled linearly according to the patient's BSA (mg/m^2). Until additional PK and safety data become available for the drug combination across a wide range of pediatric ages and body sizes, the BSA adjustment will be applied to all pediatric patients <18 years of age. For participants aged 18 years and older, based on the known PK in adults and lack of required body size adjustment, an equivalent non-BSA-based dose will be used based on the planned starting dose adjusted for an assumed adult BSA of 1.73 m^2 .

For patients aged between 6 months and 1 year, the activity of CYP3A4 is reduced by 50% compared to the typical adult population (Blake et al. 2005). Given the high variability and wide range of safe and efficacious exposures of abemaciclib in the adult population, an increase in exposures of 2-fold in patients aged 6 months to 1 year is expected to be well tolerated by the pediatric patient population. The Inclusion Criteria [1] and [2] in Study JPCS Parts A and B for body weight (at least 10 kg) and BSA (at least 0.5 m^2), and the Inclusion Criteria [3] for the disease characteristics of patients enrolled in Part C (relapsed/refractory neuroblastoma) will most likely exclude patients who are younger than 6 months of age.

Part A

The abemaciclib starting dose of $70 \text{ mg}/\text{m}^2$ BID for Part A in pediatric patients was selected based on 80% of the BSA-adjusted adult dose used for abemaciclib combination studies (that is, $150 \text{ mg BID} \div 1.73 \text{ m}^2 \times 0.8 = 70 \text{ mg}/\text{m}^2$ BID). Given the potential for patients with larger BSA to receive doses in excess of the approved adult dose, the maximum dose of abemaciclib will be capped at 150 mg BID (maximum adult combination dose).

Part B

Since Part B uses 1 less study drug, it will likely be more tolerable than the triplet combination due to fewer expected adverse events. Therefore, in Part B, one dose level higher than the MTD of abemaciclib (not to exceed 115 mg/m² BID) in Part A will be used as the starting dose in combination with temozolomide 100 mg/m²/day on Days 1 through 5 of a 21-day cycle (see Section 6.1). Starting at a higher dose level in Part B may allow the MTD to be established with fewer patients since fewer dose levels may have to be tested in the doublet escalation. Given the potential for patients with larger BSA to receive doses in excess of the approved adult dose, as with Part A, the maximum dose of abemaciclib will be capped at 150 mg BID (maximum adult combination dose).

Part C

In Part C, the MTD_A of abemaciclib of 55mg/m² in combination with irinotecan and temozolomide (determined in Part A) will be used in combination with dinutuximab and GM-CSF. If this dose level is not tolerated, a lower dose of 30 mg/m² will also be explored. This 30mg/m² dose corresponds to an adult 50 mg dose, adjusting for a typical adult BSA of 1.73 m². In adult malignancies, 50 mg abemaciclib is the lowest dose with existing clinical efficacy data.

Given the addition of dinutuximab and GM-GSF to the Part A triplet combination, the maximum dose of abemaciclib will be capped at 100 mg BID in Part C to avoid excessive exposures in the largest patients.

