5.1. Inclusion Criteria

Participants are eligible to be included in the study only if all of the following criteria apply:

Age and Weight

1. Parts A and B only:

- a. Patients must be ≤ 18 years of age at the time of study enrollment, and
- b. Body weight ≥ 10 kg and BSA ≥ 0.5 m².

Part C only:

- a. Patients must be < 21 years of age at the time of study enrollment.
- b. For patients with a starting abemaciclib dose of 30 mg/m² BID, BSA must be ≥ 0.3 m²

All Parts: the Mosteller formula should be used to calculate BSA.

2. Inclusion Criterion 2 has been deleted.

Type of Participant and Disease Characteristics

- 3. **Parts A and B only:** patients with any relapsed/refractory malignant solid tumors (excluding lymphoma), including CNS tumors, that have progressed on standard therapies. For sites that are actively enrolling Parts B and C, patients with neuroblastoma who are eligible for Part C will be excluded from Part B unless approved by Lilly CRP/CRS.

Part C only: patients with first relapse/refractory neuroblastoma. Refractory is defined as either less than partial response (PR) by INRC at the conclusion of at least 4 cycles of standard front-line induction chemotherapy or progressive disease (PD) during front-line therapy. First relapse is defined as disease recurrence following completion of aggressive multi-drug chemotherapy, surgery, autologous stem cell transplant and radiation, with or without retinoids.

NOTE: For Part C, front-line chemotherapy must have comprised 2 or more agents, including an alkylating agent and a platinum-containing compound.

For Parts A, B, and C: Patients must have at least one measurable or evaluable lesion as defined by RECIST v1.1 (Eisenhauer et al. 2009) or RANO for CNS tumors (Wen et al. 2010).

- i. Measurable is defined as a nonlymphoid soft tissue mass ≥ 1 cm (longest dimension) or lymph node ≥ 1.5 cm (short axis) on a MRI or CT scan
- ii. Evaluable disease is defined as the presence of at least one lesion, with no lesion that can be accurately measured in at least one dimension. Such lesions may be evaluable by nuclear medicine techniques, immunocytochemistry techniques, tumor markers or other reliable measures.
- iii. For CNS tumors: Isolated leptomeningeal disease in relapsed/refractory CNS tumors that is evaluable may be eligible for inclusion after consultation with the Lilly CRP/CRS.

For Part C: A tumor (either measurable or evaluable) that is either

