Appendix 8). ^{CCI} [REDACTED]

Refer to the Abemaciclib Dosing Charts in Section 10.8 (Appendix 8) for the dose rounding rules based on a patient's BSA for each dose level and if using granules, the number of granules required for each dose.

Participants taking oral granules should follow the provided instructions for the dispensing device and administration.

Until PK samples are completed on Cycle 3 Day 1, participants may only switch abemaciclib formulations (tablets to granules or vice versa) if necessary for a dose adjustment or BSA change. Following the last PK sample, participants may switch formulations as necessary (for reasons other than dose adjustment or BSA change). Oral granules and tablets can never be combined to make up a single dose.

If instructions have been provided to prepare abemaciclib in food/liquid, no other medications should be added to the food/liquid with abemaciclib.

For each cycle, the actual dose administered for all study drugs must be within 10% of the planned dose; any total cycle dose exceeding $\pm 10\%$ from the planned dose for the cycle will result in a protocol deviation. Please contact the Lilly CRP/CRS to discuss any questions for individual situations.

Investigational drugs (including abemaciclib, dinutuximab, GM-CSF, irinotecan, and temozolomide) will be supplied per local laws and regulation and country requirements.

Abemaciclib doses will be administered at approximately the same times on each day. Please see Section 10.8, Appendix 8 (Abemaciclib Dosing Chart) to determine if a change in BSA necessitates a change in abemaciclib dosing.

The planned duration of treatment is not fixed; participants will remain on study until disease progression, unacceptable toxicity, or patient withdrawal (see Section 7.1). Continuation beyond Cycle 12 will be up to the investigator's discretion and should be discussed with the Lilly.

The following treatments will be administered in 21-day cycles. Refer to Sections 1.3.1 and 1.3.2 for the daily schedule.

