8.5. Pharmacokinetics

At the visits and times specified in the SoA (Section 1.3), PK samples will be collected to determine the concentrations of:

- abemaciclib and its metabolites M2 and M20
- irinotecan and its metabolite SN-38
- temozolomide

The PK of dinutuximab and GM-CSF will not be assessed.

To ensure comprehensive PK sampling in a pediatric population, Parts A and B are designed to evaluate at least CCI [REDACTED] including at least CCI [REDACTED] and at least 2 CCI [REDACTED] If no patients CCI [REDACTED] and evaluable in the above groups, then CCI [REDACTED] will be evaluated. The number of patients 18 years of age will be capped at [REDACTED] until patient numbers in the above age groups are enrolled.

Additionally, in Part C, at least CCI [REDACTED] should be in the age group CCI [REDACTED] of age, with at least CCI [REDACTED] and at least CCI [REDACTED] [REDACTED]

Abemaciclib dosing dates and times are required to be collected 3 days prior to the PK samples. The date and exact time of collection of each PK sample must be recorded on the laboratory requisition. Beyond the first dose, PK samples may be aligned to coincide with standard laboratories when applicable, with the collection dates/times specified in the SoA (Section 1.3.3) to be used as a guide.

For patients receiving chemotherapy infusions, the PK samples should be drawn from a separate line at a peripheral access site.

A maximum of 5 samples may be collected at additional time points during the study if warranted and agreed upon between both the investigator and sponsor. Instructions for the collection and handling of blood samples will be provided by the sponsor. The actual date and time (24-hour clock time) of each sampling will be recorded.

The PK sampling schedule is designed to comply with blood volume limitations in pediatric patients. If the collection of PK samples will exceed maximum blood draw volumes for any patient, blood samples for safety will be prioritized over PK after discussion between the sponsor and the investigator.

Bioanalytical samples collected to measure investigational product concentration will be retained for a maximum of 1 year following last participant visit for the study. During this time, samples remaining after the bioanalyses may be used for exploratory analyses (such as quantification of circulating metabolites and/or protein binding work).

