10.8. Appendix 8: Abemaciclib Dosing Charts**Parts A and B:**

Dose (BID)	BSA Ranges (m ²) for each Dose Level			
	55 mg/m ²	70 mg/m ²	90 mg/m ²	115 mg/m ²
25 mg	0.50-0.68	0.50-0.53		
50 mg	0.69-1.13	0.54-0.89	0.50-0.69	0.50-0.54
75 mg	1.14-1.59	0.90-1.24	0.70-0.97	0.55-0.76
100 mg	1.60-2.04	1.25-1.60	0.98-1.24	0.77-0.97
125 mg	2.05-2.49	1.61-1.96	1.25-1.52	0.98-1.19
150 mg	2.50+	1.97+	1.53+	1.20+

Abbreviations: BID = twice daily; BSA = body surface area.

Part C:

BSA Ranges (m^2) for each Dose Level		
Dose (BID)	30mg/ m^2	55mg/ m^2
10mg	0.30-0.37 ^a	0.20
12.5mg	0.38-0.45	0.21-0.24
15mg	0.46-0.54	0.25-0.29
17.5mg	0.55-0.62	0.30-0.34
20mg	0.63-0.70	0.35-0.38
22.5mg	0.71-0.79	0.39-0.43
25mg	0.80-1.24	0.44-0.68
50mg	1.25-2.08	0.69-1.13
75mg	2.09-2.91	1.14-1.59
100mg	2.92+	1.60+

Abbreviations: BID = twice daily; BSA = body surface area.

a At the 30mg/ m^2 dose, patients must be $\geq 0.3m^2$ as a smaller BSA would require a dose that exceeds their calculated dose by $>10\%$.

Abemaciclib Oral Granules Dosing Chart			
Dose (mg)	Device Setting	# Times to Dispense	# Granules per dose
10	4	1	4
12.5	5	1	5
15	6	1	6
17.5	7	1	7
20	8	1	8
22.5	9	1	9
25	10	1	10
50	20	1	20
75	15	2	30
100	20	2	40

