### **7.2.1. Extent of Exposure**

Drug exposure, dose intensity, and drug adjustments (dose omissions and reductions) will be summarized for abemaciclib, for temozolomide, for irinotecan, for dinutuximab, and for GM-CSF where applicable. Drug exposure will include summaries of cycles received per patient, duration on therapy, and cumulative dose. Dose intensity will be calculated as the actual cumulative amount of drug taken divided by the duration of treatment. Relative dose intensity will be calculated as

$$\frac{\text{the amount of actual drug taken}}{\text{(the amount of drug prescribed)}} \times 100\%$$

(expressed as a percentage). The summary of dose adjustments and omissions will include the reason for adjustment or omission.

Extent of exposure for abemaciclib will be measured by pill counts. Dose intensity will be expressed in mg/day. The assigned cumulative dose while on study is 2 doses per day  $\times$  planned amount of drug dose (dependent on dose level and patient BSA at the beginning of each cycle)  $\times$  number of days on treatment.

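### From age 18 the protocol gives two abemaciclib dosing rules: a fixed dose at 1.73 m² in Section 4.3.1, and the patient's own BSA in Appendix 8 and the SAP; they can disagree outside BSA 1.61–1.96 m²

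*Protocol*

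**What the plan says.** Protocol Section 4.3.1 reasons from adult pharmacokinetics, where body size had no meaningful effect. It states that "the BSA adjustment will be applied to all pediatric patients <18 years of age". For participants aged 18 and over, "an equivalent non-BSA-based dose will be used based on the planned starting dose adjusted for an assumed adult BSA of" 1.73 m².

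Patients aged 18 and over can enter. Section 5.1 says for Parts A and B "Patients must be ≤ 18 years of age at the time of study enrollment" and for Part C "Patients must be < 21 years of age at the time of study enrollment". Section 8.5 expects them: "The number of patients 18 years of age will be capped at" a redacted figure until the younger age groups are filled.

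The operational text reads differently. Section 6.1 refers sites to Appendix 8 for the "dose rounding rules based on a patient's BSA for each dose level", and again to see whether a change in BSA requires a new dose. Appendix 8 ("Abemaciclib Dosing Charts") lists BSA bands against doses. It has no age column, no fixed-dose row and no footnote for age 18 and over. SAP Section 7.2.1 builds the assigned cumulative dose from the "planned amount of drug dose (dependent on dose level and patient BSA at the beginning of each cycle", also without an age exception.

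**The concern.** Section 4.3.1 states a rule to be followed, not just background, and it is the only visible place where the age-18 rule appears. A site that doses from the chart will not meet it. Two sites could therefore give different doses to patients of the same age, size and dose level, each following the protocol.

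Three things depend on this:

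- **Dose-level summaries.** DLTs, the MTD and PK are read by dose level, in cohorts of 3 to 6 during dose finding. A level could hold adults dosed under two rules without the tables showing it.
- **Deviations and reductions.** Section 6.1 counts a total cycle dose more than 10% away from plan as a deviation, so the same dose could comply under one rule and deviate under the other. Section 6.6 keys reductions to the dose at enrollment. In Part C, 100 mg leads to 75 then 50 mg, and 75 mg leads to 50 then 25 mg.
- **Exposure.** The SAP's assigned cumulative dose would not match what an adult was prescribed under Section 4.3.1.

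The protocol also does not say what happens when a patient turns 18 on study.

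**Working it through.** **Inputs.** The 1.73 m² figure and the caps (150 mg BID in Parts A and B, 100 mg BID in Part C) come from Section 4.3.1. The BSA bands come from Appendix 8. The documents give no BSA for patients aged 18 and over and no rounding rule for the fixed dose.

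**The plan's own figures reproduce.** 30 × 1.73 = 51.9 mg, which Section 4.3.1 gives as 50 mg. 150 ÷ 1.73 × 0.8 = 69.4, which it gives as 70 mg/m². The chart boundaries are midpoints of adjacent strengths divided by the dose level. At 70 mg/m², for example, (100 + 125)/2 ÷ 70 = 1.607, so the 125 mg band starts at 1.61 m².

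**Comparison.** Fixed dose = dose level × 1.73, capped, and rounded to the charted strength (assumption). Percentages are the larger dose over the smaller, minus 1.

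| Part, level (mg/m²) | × 1.73 (mg) | Fixed dose, BID | BSA where chart agrees (m²) | Chart dose at other BSA |
|---|---|---|---|---|
| A/B, 55 | 95.2 | 100 mg | 1.60–2.04 | 75 mg at 1.14–1.59 (33%); 125 mg at 2.05–2.49 (25%) |
| A/B, 70 | 121.1 | 125 mg | 1.61–1.96 | 100 mg at 1.25–1.60 (25%); 150 mg from 1.97 (20%); 75 mg at 0.90–1.24 (67%) |
| A/B, 90 | 155.7 | 150 mg (cap) | 1.53 and above | 125 mg at 1.25–1.52 (20%); 100 mg at 0.98–1.24 (50%) |
| A/B, 115 | 199.0 | 150 mg (cap) | 1.20 and above | 125 mg at 0.98–1.19 (20%) |
| C, 30 | 51.9 | 50 mg | 1.25–2.08 | 75 mg at 2.09–2.91 (50%); 25 mg at 0.80–1.24 (100%) |
| C, 55 | 95.2 | 100 mg | 1.60 and above | 75 mg at 1.14–1.59 (33%); 50 mg at 0.69–1.13 (100%) |

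The BSA range in which the chart agrees in every row is 1.61–1.96 m², which contains 1.73.

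**Range over an assumed BSA.** For 1.3–2.2 m² the non-zero differences are 20%, 25%, 33% and 50%. The 50% occurs only in Part C at 30 mg/m² from 2.09 m².

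**Against the 10% limit.** The smallest non-zero gap in the table is 125 against 150 mg. That is 25/150 = 17% low or 25/125 = 20% high, depending on which dose counts as planned. Every gap therefore exceeds 10%.

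**Assigned dose in the SAP.** Take a Part C adult at 55 mg/m² with BSA 1.50 m². Over 21 days the chart assigns 2 × 75 × 21 = 3,150 mg. The fixed rule prescribes 2 × 100 × 21 = 4,200 mg.

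**Sensitivity to rounding.** If fixed doses were rounded down to a charted strength, 95.2 would become 75 mg and 121.1 would become 100 mg. The disagreement would then move to BSA from 1.60 m² at 55 mg/m² and from 1.61 m² at 70 mg/m². It would not disappear.

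**The case against.** The strongest reply is that the passages can be read together. Section 4.3.1 is the specific rule for adults, the chart is the general tool, and reading the chart at 1.73 m² carries out Section 4.3.1. The defect would then be a missing footnote rather than two competing designs. That is a fair account of what may have been intended. But nothing visible in Section 6.1 or Appendix 8 tells a site to do this, and Section 6.1 asks for re-dosing when BSA changes, which has no meaning under a fixed dose.

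A second reply is that text is redacted in Section 6.1 just before the chart reference, and an instruction for age 18 could be there. This stands as a limit on what can be said about Section 6.1. It would not change the printed charts or the SAP formula.

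A third reply is that few patients are involved: only age 18 in Parts A and B, temporarily capped in number, and 18 to 20 in Part C. In Part C at 55 mg/m², only those below 1.60 m² are affected. This stands too. The number cannot be derived from the documents.

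**Conclusion.** The plan is wrong as written: this is an internal inconsistency in an operative dosing rule. Assuming the fixed dose is rounded to the charted strength, the two rules agree at every level for BSA 1.61–1.96 m² and can differ outside it, by 20–50% where they differ over an assumed 1.3–2.2 m².

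Three stronger readings are tempting, and the documents do not support them:

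- **That every adult is dosed 20–67% differently under the two rules.** The gap is zero for the protocol's own typical adult of 1.73 m². The 67% needs 70 mg/m² with BSA 0.90–1.24 m². It is not the ceiling either, since very small adults could reach 100%.
- **That an adult correctly given the fixed dose would show a relative dose intensity of 4,200/3,150 = 133%.** SAP Section 7.2.1 divides drug taken by drug prescribed. Only the separate assigned cumulative dose depends on BSA, and the SAP does not say that it is the denominator. The supportable statement is that the assigned dose does not carry the age-18 rule.
- **That the MTD is distorted.** With 3 to 6 patients per cohort, one adult dosed under the other rule could matter, but nothing shows that this occurred.

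Which rule is right is for the sponsor to decide.

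**What to change.** - Reconcile Protocol Sections 4.3.1 and 6.1 and Appendix 8 so that one rule, chosen by the sponsor, applies from age 18. Print it in both the Parts A/B and the Part C charts, with the rounding if a fixed dose is kept.
- State how a patient who turns 18 on study is handled.
- Carry the same rule into the assigned cumulative dose in SAP Section 7.2.1, and say whether that quantity or the prescribed dose is the denominator of relative dose intensity.
- Identify patients aged 18 and over already treated, and tabulate the dose actually given beside the dose level in the DLT and PK summaries.

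The cost is an amendment line, a chart row or footnote, a SAP formula edit and one added column in the tables. No new data or patients are needed.
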